4.5. Sponsor's Qualified Medical Personnel

The contact information for the sponsor's appropriately qualified medical personnel for the study is documented in the study contact list located in the supporting study documentation.

To facilitate access to appropriately qualified medical personnel on study-related medical questions or problems, subjects are provided with a contact card. The contact card contains, at a minimum, protocol and investigational product identifiers, subject study numbers, contact information for the investigator site, and contact details for a contact center in the event that the investigator site staff cannot be reached to provide advice on a medical question or problem originating from another healthcare professional not involved in the subject's participation in the study. The contact number can also be used by investigator staff if they are seeking advice on medical questions or problems; however, it should be used only in the event that the established communication pathways between the investigator site and the study team are not available. It is therefore intended to augment, but not replace, the established communication pathways between the investigator site and the study team for advice on medical questions or problems that may arise during the study. The contact number is not intended for use by the subject directly, and if a subject calls that number, he or she will be directed back to the investigator site.

5. INVESTIGATIONAL PRODUCTS

For the purposes of this study, and per International Council for Harmonisation (ICH) guidelines, investigational product is defined as a pharmaceutical form of an active ingredient or placebo being tested or used as a reference/comparator in a clinical trial, including a product with a marketing authorization when used or assembled (formulated or packaged) in a way different from the approved form, or when used for an unapproved indication, or when used to gain further information about an approved use (ICH E6 1.33).

For this study, the investigational product is 13vPnC.

5.1. Allocation to Investigational Product

This is a Phase 4, single-arm, open-label study.

5.2. Subject Compliance

All doses of investigational product will be administered by the appropriately designated study staff at the investigator site.

5.3. Investigational Product Supplies

Commercial 13vPnC will be provided by the sponsor to each study site. The vaccine will be labeled in accordance with local regulations.

5.3.1. Dosage Form and Packaging

13vPnC contains saccharides from pneumococcal serotypes 1, 3, 4, 5, 6A, 6B, 7F, 9V, 14, 18C, 19A, 19F, and 23F individually conjugated to nontoxic diphtheria toxin cross-reactive material 197 (CRM₁₉₇). The vaccine is formulated to contain 2.2 µg of each saccharide, except for 4.4 µg of 6B, per 0.5-mL dose. The vaccine contains 5 mM succinate buffer, 0.85% sodium chloride, 0.02% polysorbate 80, and 0.125 mg aluminum as aluminum phosphate, per 0.5-mL dose.

13vPnC will be provided as a 0.5-mL dose in a prefilled syringe.

5.3.2. Preparation and Dispensing

Only appropriately qualified personnel should dispense the investigational product.

5.3.3. Administration

At Visit 1, all subjects will receive a single dose (0.5 mL) of 13vPnC intramuscularly in the left thigh or the left deltoid muscle as appropriate for the subject.

Standard vaccination practices must be observed and vaccine must not be injected into blood vessels. Appropriate medication and other supportive measures for management of an acute hypersensitivity reaction should be available in accordance with local guidelines for standard immunization practices.

Administration of investigational products should be performed by an appropriately qualified, Good Clinical Practice (GCP)-trained, and vaccine-experienced member of the study staff (eg, physician, nurse, physician's assistant, nurse practitioner, pharmacist, or medical assistant) as allowed by local, state, and institutional guidance.

Investigational product administration details will be recorded on the case report form (CRF).

5.4. Investigational Product Storage and Accountability

5.4.1. Investigational Product Storage

13vPnC will be shipped at +2°C to +8°C to each study site upon request. Upon receipt at the study site, the vaccines should be immediately transferred to a +2°C to +8°C temperature-monitored refrigerator for storage.

The investigator or an approved representative, eg, pharmacist, will ensure that all investigational products are stored in a secured area with controlled access under required storage conditions and in accordance with applicable regulatory requirements.

Investigational products should be stored in their original containers and in accordance with the labels.

Any storage conditions stated in the SRSD will be superseded by the storage conditions stated on the product label.

Site systems must be capable of measuring and documenting (for example, via a log), at a minimum, daily minimum and maximum temperatures for all site storage locations (as applicable, including frozen, refrigerated, and/or room-temperature products). This should be captured from the time of investigational product receipt throughout the study. Even for continuous-monitoring systems, a log or site procedure that ensures active evaluation for excursions should be available. The intent is to ensure that the minimum and maximum temperature is checked each business day to confirm that no excursion occurred since the last evaluation and to provide the site with the capability to store or view the minimum/maximum temperature for all nonworking days upon return to normal operations. The operation of the temperature-monitoring device and storage unit (for example, refrigerator), as applicable, should be regularly inspected to ensure they are maintained in working order.

Any excursions from the product label storage conditions should be reported to Pfizer upon discovery. The site should actively pursue options for returning the product to the storage conditions described in the labeling, as soon as possible. Deviations from the storage requirements, including any actions taken, must be documented and reported to Pfizer.

Once an excursion is identified, the investigational product must be quarantined and not used until Pfizer provides permission to use the investigational product. It will not be considered a protocol deviation if Pfizer approves the use of the investigational product after the temperature excursion.

Use of the investigational product prior to Pfizer approval will be considered a protocol deviation. Specific details regarding information the site should report for each excursion will be provided to the site.

Receipt of materials, door opening and closing, and other routine handling operations where the products are briefly out of the temperature range described in the labeling are not considered excursions.

5.4.2. Investigational Product Accountability

The investigator site must maintain adequate records documenting the receipt, use, loss, or other disposition of the investigational product supplies. All investigational products will be accounted for using a drug accountability form/record.

5.4.3. Destruction of Investigational Product Supplies

The sponsor or designee will provide guidance on the destruction of unused investigational product (eg, at the site). If destruction is authorized to take place at the investigator site, the investigator must ensure that the materials are destroyed in compliance with applicable environmental regulations, institutional policy, and any special instructions provided by Pfizer, and all destruction must be adequately documented.

5.5. Concomitant Medication(s)

5.5.1. Prohibited During the Study

The following are prohibited during the study:

- Vaccination with any licensed or investigational pneumococcal vaccine other than that specified by the protocol.
- Receipt of any other investigational product.

5.5.2. Permitted During the Study

The following are permitted during the study:

- Any other vaccine may be given according to local practice. If any vaccine other than 13vPnC is administered during the study, the name and date of administration will be documented in the CRF.
- Any medication, except those listed in [Section 5.5.1](#), is permitted but will not be documented in the CRF.

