4.3. Criteria for Temporarily Delaying Vaccine Administration

The following conditions are temporary or self-limiting and a subject may be vaccinated in the study once the condition has resolved and no other exclusion criteria are met.

1. Current febrile illness (temperature $\geq 100.4^{\circ}\text{F}$ [38.0°C]) or other acute illness within 48 hours before 13vPnC administration.

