6.1. Visit 1 - Vaccination (Day 1)

- Obtain written informed consent and, if applicable, assent (age dependent on local requirement) before performing any study-specific procedures.
- Assign a subject identification number.
- Obtain and record the subject demography (including date of birth, sex, race, and ethnicity).
- Obtain and record any nonstudy vaccinations received from 28 days prior to vaccination.
- Obtain and record the medical history, including the presence of chronic conditions and/or medical history of significance.
- Perform physical examination evaluating any clinically significant abnormalities, including worsening of medical history conditions, within the following body systems: general appearance; skin; head, eyes, ears, nose, and throat; heart; lungs; abdomen; musculoskeletal; extremities; neurological; and lymph nodes.
- Collect and record any AEs and serious adverse events (SAEs) that occurred since the signing of the ICD.
- Perform a urine pregnancy test on female subjects of childbearing potential.
- Confirm use of appropriate contraceptives (if appropriate).
- On the day of vaccination, prior to vaccination, measure and record the subject's temperature using the preferred local method.
- Ensure that all of the inclusion criteria, none of the exclusion criteria, and none of the temporary delay criteria are met.
- Administer a single 0.5-mL injection of 13vPnC into the left thigh or the left deltoid muscle as appropriate for the subject.
- Observe the subject for at least 20 minutes after 13vPnC administration for any acute reactions. Record any AEs in the subject's source documents and on the AE section of the CRF.
- Issue an e-diary and provide instructions on its use for 7 days (Day 1 through Day 7, where Day 1 is the day of vaccination).
- Issue a measuring device and a digital thermometer and provide instructions on their use for 7 days (Day 1 through Day 7, where Day 1 is the day of vaccination).

- Ask the parent(s)/legal guardian(s)/caregiver(s) to contact the site staff or investigator immediately if the subject experiences redness or swelling at the injection site measuring greater than 7 cm (>14 measuring device units) from Day 1 to Day 7 after vaccination to determine if an unscheduled reactogenicity visit is required.
- Ask the parent(s)/legal guardian(s)/caregiver(s) to contact the investigator immediately if any significant illness or hospitalization occurs during the study period.

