6.2. Visit 2 - Follow-up Visit (28 to 42 Days After Visit 1)

- Review the subject's e-diary data and collect the e-diary. Collect stop dates of any e-diary events ongoing on the last day that the e-diary was completed and record stop dates in the CRF.
- Determine whether any AEs (including SAEs) have occurred since the last study visit and record them on the CRF (see [Section 8](#)).
- Collect and record any follow-up information on previously documented AEs and SAEs and record their end dates or confirm that they are still continuing.
- Record any nonstudy vaccinations.
- Confirm use of appropriate contraceptives (if appropriate).
- Complete the source documents and the CRFs.

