8.1.5. Causality Assessment

The investigator's assessment of causality must be provided for all AEs (serious and nonserious); the investigator must record the causal relationship on the CRF, and report such an assessment in accordance with the SAE reporting requirements, if applicable. An investigator's causality assessment is the determination of whether there exists a reasonable possibility that the investigational product caused or contributed to an AE; generally the facts (evidence) or arguments to suggest a causal relationship should be provided. If the investigator does not know whether or not the investigational product caused the event, then the event will be handled as "related to investigational product" for reporting purposes, as defined by the sponsor. If the investigator's causality assessment is "unknown but not related" to investigational product, this should be clearly documented on study records.

In addition, if the investigator determines that an SAE is associated with study procedures, the investigator must record this causal relationship in the source documents and CRF, and report such an assessment in the dedicated section of the CT SAE Report Form and in accordance with the SAE reporting requirements.

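### Since other vaccines may be given at any time around 13vPnC, does the SAP need an analysis of systemic events by nonstudy vaccination?

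*Protocol*

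**What the plan says.** Protocol 5.5.2: "Any other vaccine may be given according to local practice", and for any such vaccine given during the study "the name and date of administration will be documented in the CRF". Protocol 5.5.1 bars other pneumococcal vaccines and "Receipt of any other investigational product". The only grounds in Protocol 4.3 for postponing the dose are febrile illness or "other acute illness within 48 hours before 13vPnC administration". Recent vaccination is not among them, and the exclusion criteria set no interval either.

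Recording starts before the dose and runs to the end of follow-up. At Visit 1 the site is to "Obtain and record any nonstudy vaccinations received from 28 days prior to vaccination" (Protocol 6.1). At Visit 2, 28 to 42 days later, it is to "Record any nonstudy vaccinations" (Protocol 6.2).

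SAP 3.5.3 codes these vaccines by dictionary, and SAP 6.3.6 tabulates the number and percentage of recipients by ATC class, with no period named. SAP 6.3.1 (AEs), 6.3.2 (reactogenicity) and 6.3.4 (immediate AEs) summarize the whole safety population. None of them splits or flags by another vaccine.

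**The concern.** The only objective is to describe the safety profile of 13vPnC, and there is no control arm. Fever, fatigue, headache and muscle pain are not specific to one vaccine. A subject given another vaccine at the same visit, or a day or two either side, contributes any resulting symptoms to the 13vPnC tables.

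The other two endpoint groups are better protected. Local reactions are read at the 13vPnC injection site (Protocol 7.3.1). Each AE carries an investigator causality assessment (Protocol 8.1.5) and appears in a listing (SAP 6.3.1). E-diary systemic events have neither safeguard.

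The table in SAP 6.3.6 has no time split, so it cannot show how many diary weeks overlapped another vaccination. At stake is whether a reader can take the systemic-event rates as those of 13vPnC alone.

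**Working it through.** **1. The plan's own figure.** Protocol Table 4 gives 63.4% as the chance of seeing at least one AE with a 1.0% true rate and N = 100. Check: 1 − (1 − 0.01)^100 = 63.4%. It reproduces. The sample size is justified by the chance of detecting events, not by comparing subgroups or attributing cause.

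**2. What is being estimated.** SAP 3.1 defines the endpoint by time since vaccination, not by cause. SAP 5.1 states that there are no hypotheses or decision rules. The proportion of all vaccinated subjects with an event is therefore the intended quantity, in a population vaccinated under local practice.

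**3. What the SAP 6.3.6 count can tell.** SAP 6.3.6 names no period. The natural reading is the whole recording period:

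- shortest: 28 + 1 + 28 = 57 days
- longest: 28 + 1 + 42 = 71 days

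A window of 7 days before the dose through Day 7 is 14 days. If other vaccinations were spread evenly (assumption), 14/71 = 19.7% to 14/57 = 24.6% of them would fall in it. Same-visit vaccination would raise that share. On this reading the count is also an upper bound: the number vaccinated near dosing cannot exceed the number vaccinated at any time. A small count in SAP 6.3.6 settles the question, and a large one tells the analyst to look at dates.

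**4. Size of the shift.** Let p0 be the event rate without another vaccine, k the share of subjects vaccinated near dosing, and RR the risk ratio in them. The documents give none of these.

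Pooled rate = (1 − k) × p0 + k × p0 × RR, with p0 = 10%:

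- k = 5%, RR = 1.5: 9.5% + 0.75% = 10.25%, a shift of 0.25 points
- k = 20%, RR = 2: 8% + 4% = 12.0%, a shift of 2.0 points

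The Clopper-Pearson 95% CI for 10/100 is 4.9% to 17.6%.

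**5. Harsher assumptions.** Keep the 10% base and add an absolute excess in the co-vaccinated:

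| Share co-vaccinated | Excess (points) | Pooled rate | 95% CI, n = 100 |
|---|---|---|---|
| 5% | 10 | 10.5% | 5.6% to 18.8% (11/100) |
| 20% | 20 | 14.0% | 7.9% to 22.4% |
| 30% | 30 | 19.0% | 11.8% to 28.1% |

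With shares of 5%, 10%, 20% and 30% and excesses of 10, 20 and 30 points, the interval still covers 10% in 11 of 12 combinations. The exception is the last row, where 30 of 100 subjects are co-vaccinated and have four times the base risk (40% against 10%). Coverage does not show an absence of bias. It puts the shift on the scale of the precision available.

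**6. Would an added table settle it?** Suppose it excluded everyone vaccinated near dosing. With 20% observed throughout, the intervals are 12.7% to 29.2% (20/100), 12.5% to 29.5% (19/95) and 11.9% to 30.4% (16/80). These nearly coincide, so a difference of a point or two could not be distinguished from chance.

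Excluding subjects vaccinated on Days 2 to 7 also conditions on something after the dose. If symptoms delay a later vaccine, those excluded are the healthier ones, and the remaining rate is pushed up. Flagging every AE that follows a nonstudy vaccine has a different flaw: with no time limit, a vaccine given 28 days before the dose would flag every later AE in that subject.

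**The case for a change.** The best case for a change is that this study exists to collect what the earlier Indian study lacked, namely e-diary reactogenicity (Protocol 1.2). With no control arm, overlap with another vaccine is a plain competing explanation for a systemic event. The dates of vaccines given during the study are already collected, so a listing would cost almost nothing. A window is also best fixed before anyone sees data, because the study is open-label and the sponsor may review data while it runs (Protocol 9.3).

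Part of this stands. No stated output shows how many subjects had another vaccine near the diary week, and a listing would be a reasonable courtesy to the reader. The rest does not make the plan deficient. Nothing in the documents shows that any subject will be vaccinated near dosing. With no test or decision rule, a window chosen later cannot distort a formal conclusion, and the pooled rate remains the reported result.

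A worry that dates of pre-dose vaccines might be missing is weak. A site cannot apply the 28-day limit in Protocol 6.1 without knowing when the vaccine was given, though the CRF itself is not among the documents. Two other sources are also not supplied: the sponsor reporting standards to which SAP 6.3 defers, and the local package insert. Either may already cover part of the point.

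**Conclusion.** The observation is accurate, but it asks for an extra supporting output and does not identify an error. Pooling is the stated descriptive endpoint, no decision depends on the rates, and AEs and local reactions have their own safeguards. The shift is 0.25 to 2.0 points under moderate assumptions and up to 9 points (19.0% against 10%) in the most extreme combination examined. The base rate, the share co-vaccinated and the excess risk are all assumed, so the true size is unknown.

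This is a gap that analysts can fill sensibly. If the SAP 6.3.6 table shows more than a few recipients, the team can list those vaccinated close to Day 1 with the vaccine, its timing and any e-diary systemic events, using data the protocol already collects. If it shows few, nothing is needed. The plan can stand as written.

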6. STUDY PROCEDURES

The schedule of procedures for individual study participation is summarized in the Schedule of Activities. In order that the study visits are scheduled within the correct time frames, the day of vaccination should be considered Day 1.

6.1. Visit 1 - Vaccination (Day 1)

- Obtain written informed consent and, if applicable, assent (age dependent on local requirement) before performing any study-specific procedures.
- Assign a subject identification number.
- Obtain and record the subject demography (including date of birth, sex, race, and ethnicity).
- Obtain and record any nonstudy vaccinations received from 28 days prior to vaccination.
- Obtain and record the medical history, including the presence of chronic conditions and/or medical history of significance.
- Perform physical examination evaluating any clinically significant abnormalities, including worsening of medical history conditions, within the following body systems: general appearance; skin; head, eyes, ears, nose, and throat; heart; lungs; abdomen; musculoskeletal; extremities; neurological; and lymph nodes.
- Collect and record any AEs and serious adverse events (SAEs) that occurred since the signing of the ICD.
- Perform a urine pregnancy test on female subjects of childbearing potential.
- Confirm use of appropriate contraceptives (if appropriate).
- On the day of vaccination, prior to vaccination, measure and record the subject's temperature using the preferred local method.
- Ensure that all of the inclusion criteria, none of the exclusion criteria, and none of the temporary delay criteria are met.
- Administer a single 0.5-mL injection of 13vPnC into the left thigh or the left deltoid muscle as appropriate for the subject.
- Observe the subject for at least 20 minutes after 13vPnC administration for any acute reactions. Record any AEs in the subject's source documents and on the AE section of the CRF.
- Issue an e-diary and provide instructions on its use for 7 days (Day 1 through Day 7, where Day 1 is the day of vaccination).
- Issue a measuring device and a digital thermometer and provide instructions on their use for 7 days (Day 1 through Day 7, where Day 1 is the day of vaccination).

- Ask the parent(s)/legal guardian(s)/caregiver(s) to contact the site staff or investigator immediately if the subject experiences redness or swelling at the injection site measuring greater than 7 cm (>14 measuring device units) from Day 1 to Day 7 after vaccination to determine if an unscheduled reactogenicity visit is required.
- Ask the parent(s)/legal guardian(s)/caregiver(s) to contact the investigator immediately if any significant illness or hospitalization occurs during the study period.
- Schedule an appointment for the next study visit.
- Remind the parent(s)/legal guardian(s)/caregiver(s) to bring the e-diary to the next study visit.
- The investigator or an authorized designee completes the source documents, completes the CRF, and updates the investigational product accountability records.
- The investigator or appropriately qualified designee reviews the e-diary data online at frequent intervals (daily is optimal) for the 7 days following vaccination to evaluate subject compliance and as part of the ongoing safety review.

